### 4.10. Sample Size

Based on our preliminary data, co-ingestion of galactose increased postprandial plasma triglyceride incremental area under the curve by a further  $46.51 \pm 0.28$  mmol·L x 300 min (mean  $\pm$  SD) above glucose. Using this effect size (d = 0.75), 24 participants would provide a >90% probability (power = 0.94) of detecting such an effect with an  $\alpha$ -level of 0.05 using a one-way, repeated-measures ANOVA and accounting for post-hoc comparisons of three factors by the principle of closed testing. Accordingly, 24 adults will be recruited. **Dropouts will be replaced in a rolling fashion to ensure a complete sample size of 24. Based on our previous experience of similar studies, we expect a dropout rate of ~20% and thus anticipate recruitment of ~28 people to achieve this target.** 

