# 3. AIMS, OBJECTIVES AND HYPOTHESIS

**PRIMARY AIM:** To understand the effect and mechanism of lactose on postprandial lipaemia in men and women by addressing the following research objectives (RO):

- RO1 determine to what extent ingestion of lactose exaggerates postprandial triglycridaemia
- RO2 determine the effect of lactose ingestion on hepatic fatty acid synthesis (de novo lipogenesis)
- RO3 determine the degree to which lactose ingestion alters dietary fat oxidation

**HYPOTHESIS:** Lactose co-ingestion with a high-fat meal will exaggerate postprandial lipaemia and stimulate hepatic fatty acid synthesis (*de novo* lipogenesis) to a similar extent to sucrose ingestion, and a greater extent than glucose polymer co-ingestion, whilst suppressing dietary fat oxidation.

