#### Primary analyses

Summary statistics (e.g. iAUC, AUC, peak concentrations) will be analysed by one-way ANOVA. Time-course data will be assessed by a two-way (time x treatment) ANOVA. Paired t-tests will be used for post-hoc comparisons, which will be corrected for multiple comparisons using the Holm-Bonferonni adjustment.

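### Section 4.10: the printed pilot mean and SD cannot give d = 0.75, and the power of 0.94 is stated for closed testing whereas 4.11 plans Holm-adjusted paired t-tests

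*Combined protocol and SAP*

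**What the plan says.** Section 4.10 (Sample Size) gives the pilot increment in triglyceride iAUC, galactose above glucose, as 46.51 ± 0.28 mmol/L x 300 min, labelled mean ± SD. It treats this as the planning effect: "Using this effect size (d = 0.75), 24 participants would provide a >90% probability (power = 0.94) of detecting such an effect". The test is described as at an alpha "level of 0.05 using a one-way, repeated-measures ANOVA", "accounting for post-hoc comparisons of three factors by the principle of closed testing". The recruitment target of 24 follows directly from this statement.

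Section 4.11 (Primary analyses) describes the pairwise step differently: "Paired t-tests will be used for post-hoc comparisons, which will be corrected for multiple comparisons using the Holm-Bonferonni adjustment".

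Section 4.2 makes lactose versus maltodextrin the primary contrast. Section 3 gives the only indication of where sucrose is expected to lie: lactose will raise lipaemia "to a similar extent to sucrose ingestion, and a greater extent than glucose polymer co-ingestion". The documents do not give the sidedness of the test, a within-person correlation, a numerical sucrose response or a derivation of d.

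**The concern.** There are two separate problems.

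First, the text presents d = 0.75 as the effect size of the pilot increment printed just before it, yet the ratio of that mean to that SD is more than two hundred times larger. Since d is the only stated basis for 24 participants, a reader cannot check the sample size.

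Second, the power belongs to a named multiplicity procedure, and the analysis section names another. With three drinks, ANOVA-gated closed testing compares each pair at the full 0.05 once the overall test rejects. Holm compares the smallest of three p-values with 0.05/3, the next with 0.05/2 and the last with 0.05. The two procedures do not have the same power for the primary contrast. At stake is whether the claim of more than 90% applies to the analysis that will be run.

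**Working it through.** **Inputs.** From 4.10: mean 46.51, SD 0.28, d = 0.75, n = 24, alpha 0.05, power 0.94. From 4.11: Holm-adjusted paired t-tests. From section 3: sucrose similar to lactose, both above maltodextrin. Assumed, because the documents do not say: two-sided testing, d as the paired effect size (mean/SD of within-person differences), normal data, equal variances and sphericity.

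**1. Effect size from the printed figures**

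- d = mean/SD = 46.51/0.28 = 166.1, against 0.75 stated.
- SD needed for d = 0.75 with the printed mean: 46.51/0.75 = 62.0, and 62.0/0.28 is about 221.
- Mean needed for d = 0.75 with the printed SD: 0.75 x 0.28 = 0.21.

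Simple repairs that were tried:

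- 0.28 as an SEM, with n = 10 as in the Figure 1 legend: SD = 0.28 x √10 = 0.885, so d = 46.51/0.885 = 52.5.
- 0.28 in mmol/L, with the mean divided by 300 min: (46.51/300)/0.28 = 0.155/0.28 = 0.55.

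Neither gives 0.75.

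**2. Reproducing the stated power, taking d = 0.75 as given**

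A single unadjusted paired t-test has df = 23, noncentrality 0.75 x √24 = 3.674 and two-sided critical value 2.069. Power = 0.940, which agrees with the stated 0.94.

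**3. Power for lactose versus maltodextrin under each multiplicity procedure**

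Three-treatment crossover trials with n = 24 were simulated, at least 200,000 per case. The SD of every pairwise difference was 1, and lactose minus maltodextrin was 0.75. The sucrose mean was placed on the same scale, with maltodextrin at 0. Closed testing means that the repeated-measures ANOVA and the paired t-test are both significant at 0.05. Holm is applied over the three paired t-tests.

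| Sucrose mean | Closed testing | Holm |
|---|---|---|
| 0.75 (equal to lactose) | 0.93 | 0.88 |
| 0 (equal to maltodextrin) | 0.93 | 0.88 |
| 0.375 (midway) | 0.89 | 0.86 |
| 0.85 | 0.94 | 0.89 |
| 1.0 (one third above the lactose effect) | 0.94 | 0.90 |
| 1.25 | 0.94 | 0.93 |

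The pattern is symmetric: sucrose at -0.25, below maltodextrin, also gives 0.94 and 0.90, but that is contrary to the hypothesis in section 3. For reference, a paired t-test at 0.05/3 gives 0.853.

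**4. Comparison with the claim**

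With sucrose equal to lactose, closed testing keeps power above 90% and Holm does not. Holm loses about 0.93 - 0.88 = 5 points against closed testing, and 0.94 - 0.88 = 6 points against the stated value.

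**The case against.** The strongest reply has three parts.

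**The power figure is defensible on its own terms.** A reader might infer that 0.94 matches only an unadjusted paired t-test, and so that multiplicity was ignored. The documents do not support this. ANOVA-gated closing gives 0.93 with sucrose equal to lactose and 0.94 with sucrose somewhat above it. A value close to the unadjusted one is what that procedure should give with three treatments. This part stands. What remains is that 4.11 plans a different procedure.

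**The Holm figures depend on sucrose.** This also stands. Section 3 says similar, not equal, and gives no number. The values 0.86 and 0.88 are examples and not bounds: Holm reaches 0.90 with sucrose one third above the lactose effect and 0.93 at 1.25. The shortfall is therefore conditional, although it applies under the most direct reading of the plan's own hypothesis.

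**The ratio of 166 may overstate the slip.** It assumes that mean and SD share a unit. Suppose instead that 0.28 is in mmol/L and is also a per-condition SD. Then a within-person correlation of about 0.73 gives a paired d of 0.55/√(2 x (1 - 0.73)) = 0.75. The documents give neither that reading nor that correlation, so this is only a possible explanation. It does show that a unit or label slip could account for the gap, and that d itself need not be wrong. The printed line still needs correcting.

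**Conclusion.** The point holds in two parts of different strength.

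The mismatch in the effect size is certain: the mean, SD, unit or label, and d in 4.10 cannot all be right as printed. The documents do not show which one is wrong.

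The second part is conditional. Given d = 0.75, n = 24, two-sided alpha 0.05, equal variances and sphericity, the Holm analysis in 4.11 has power of about 0.88 if sucrose equals lactose and 0.86 if it lies midway. Within the ordering that section 3 expects, the stated claim of more than 90% is not met unless sucrose clearly exceeds lactose. Under the closed testing named in 4.10 the claim is met with sucrose equal to lactose (0.93), and narrowly missed with sucrose midway (0.89).

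A reader might go on to conclude that 24 participants are too few. The documents do not show that. If d is really 0.75, power is 0.86 or more in every case computed here; if d is something else, the direction of the error is unknown. The defect is that the planned power cannot be verified as written, and that 4.10 and 4.11 do not describe the same procedure. It should be fixed.

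**What to change.** 1. From the pilot data already held, recompute the mean and SD of the within-person iAUC difference (galactose minus glucose). Print mean, SD and d in 4.10 in one unit, so that d = mean/SD, with the pilot n. If d was derived in another way, for example from per-condition SDs and a correlation, state those inputs.
2. Restate the power for n = 24 from that d, for lactose versus maltodextrin under the Holm procedure in 4.11. Give alpha, sidedness and the sucrose response assumed.
3. Name the same multiplicity procedure in 4.10 and 4.11.

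The cost is one recalculation and a few lines of text. No extra participants or measurements are requested. The downside is that the restated power may be below 0.94.

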#### 4. PROGRAMME AND METHODOLOGY

#### 4.1. Study Design

This research will involve a randomised, double-blind, crossover study that will assess the acute postprandial metabolic responses to three different test drinks. All three test drinks will be comprised of a high-fat milkshake with the addition of either maltodextrin, sucrose or lactose. Individuals will be required to attend the laboratories for a preliminary visit, followed by the three laboratory trial days, with a washout period of 28±7 days.

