# 4.2. Primary Outcome

The effect of lactose *versus* maltodextrin co-ingestion on postprandial incremental area under the curve (iAUC) for plasma triglyceride concentrations (6-hour postprandial period).

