#### 4.7. Screening

Participants will be invited to the University of Bath to provide informed consent, and thereafter will be invited to undertake the assessments of eligibility listed below. Given the range of screening measurement required, these measurements may take place over more than one visit. As all potential participants will be offered feedback from the screening, in the event that a potential participant be deemed ineligible for the study based on a single measurement, the individual will be informed immediately and the subsequent screening measures will only be carried out at the participant's request.

**General health status:** Suitability to participate (e.g. menopausal status, pregnancy etc.) and other practical screening questions (e.g. any reason why participants could not complete the study within a reasonable time-frame etc.) will be self-reported by the participant via a health screen questionnaire. Food allergies and intolerances will be reported in this questionnaire to ensure that participants are able and willing to consume the test drinks.

**Anthropometrics:** Body mass will be measured using digital scales and height using a stadiometer. Body mass index (BMI) will be calculated by dividing body mass (kg) by height (m) squared. Waist circumference (cm) will be measured at the narrowest point between the lowest rib and iliac crest, and hip circumference (cm) will be measured at the widest point of the gluteal using a tape measure.

**Body composition (DXA):** The participant will be positioned supine in a dual-energy x-ray absorptiometry (DXA) scanner with their extremities within limits indicated and not touching their torso if possible. Fat mass (kg), lean mass (kg), body fat percentage (%) and bone mineral density (g/cm²) will be measured. Fat mass index will be calculated by dividing fat mass (kg) by height (m) squared.

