### 4.12. Storage and Management of Data

Blood samples will be partially processed on the day of collection before freezing in preparation for analysis. Throughout this period and during the subsequent analysis, blood and breath samples will be kept in a locked laboratory and will be inaccessible to anyone outside of the research team. Samples will be coded and identified only using anonymized sample identifier numbers. After analysis, samples will be stored until the work has been published. We will ask participants to consent to their samples being used in any other ethically approved project during the lifetime of the current project.

Some analyses will be required to be performed at other sites (e.g. University of Oxford for Mass Spectrometry). These samples will be coded and identified only using anonymized sample identifier numbers for shipment.

If a participant wishes to withdraw from the study, they will be permitted to do so, however their samples will only be destroyed by specific request of the participant. Withdrawing participants will be reminded of this at the point of withdrawal, and should they not wish that their samples not be analysed or further stored, said samples will be destroyed immediately.

Any results published from this study will be anonymous and include no identifiable information. An Excel data sheet maintained on a University computer will be used to record participant information and results. The computer will be password protected to ensure only the designated researchers can access the data.

Whilst all measurements included in the protocol provide insight into physiology and health, of those that have recognised clinical significance and established normal ranges, only bone mineral density from DEXA can be provided in a clinically meaningful timeframe. As such, should a participant's data for this measure fall outside clinically normal ranges, we will inform the participant's GP directly by way of a letter, provided the participant has consented for us to do so.

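### If the 100 g lactose drink drives some dropout, the 24 completers are enriched for people who tolerate it, and no planned analysis or report would show this

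*Combined protocol and SAP*

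**What the plan says.** **Screening.** The exclusion criteria in section 4.5 name lactose intolerance. Section 4.7 relies on a self-completed health questionnaire to find it: "Food allergies and intolerances will be reported in this questionnaire to ensure that participants are able and willing to consume the test drinks". No tolerance test is among the listed screening assessments.

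**Exposure.** In section 4.8 each drink has 50 g of fat and 100 g of one carbohydrate. Lactose is that carbohydrate in one drink only, and the protocol itself calls the quantity very high.

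**Dropout.** Section 4.10 says "Dropouts will be replaced in a rolling fashion to ensure a complete sample size of 24". It expects about 20% dropout, on the basis of similar studies, and recruitment of about 28 people. Reason, period and drink are not distinguished.

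**Analysis.** Section 4.11, under primary analyses, says "Summary statistics (e.g. iAUC, AUC, peak concentrations) will be analysed by one-way ANOVA", followed by Holm-adjusted paired t-tests. The power statement in section 4.10 makes clear that the ANOVA is a repeated-measures one. No analysis set, rule for partial completers or sensitivity analysis is given.

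**Samples.** For people who withdraw, section 4.12 says "their samples will only be destroyed by specific request of the participant". The material for analysing their completed visits is therefore normally kept, but no analysis of it is planned.

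**The concern.** Someone who malabsorbs lactose without knowing it, or who has no trouble at everyday intakes, can pass the questionnaire and first find out at the 100 g visit. If that visit makes the person leave, dropout depends on the response to the arm under test. The person is replaced, and a repeated-measures analysis of 24 complete participants does not include them.

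The primary objective asks to what extent lactose raises postprandial triglycerides, so the size of the effect matters as well as its significance. If leavers would have responded differently from stayers, the completer estimate describes a group partly selected by its reaction to the drink. The text of sections 4.8 and 4.9 includes no record of gastrointestinal symptoms or of drinks left unfinished, and section 4.11 plans no table of withdrawals. A reader of the results could not tell whether any of this had happened.

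**Working it through.** **1. The plan's own figures.** Inputs from section 4.10: d = 0.75, n = 24, alpha 0.05, power 0.94. A two-sided paired t-test with 23 degrees of freedom and noncentrality 0.75 × √24 = 3.67 gives power 0.940, which matches. For recruitment, 24/(1 − 0.20) = 30 and 24 × 1.20 = 28.8. The stated figure of about 28 implies a loss of 4/28 = 14.3%. I therefore carry both 4 of 28 and 6 of 30.

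**2. What replacement does.** Without it, 24 × 0.80 ≈ 19 completers would remain, with power 0.87. A complete-case analysis of those 19 would be selected in the same way. Replacement restores power and does not create the selection; the analysis set does.

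**3. Size under assumptions.** Let p be the share of enrolled people who leave because of the lactose drink. Let r be their lactose-maltodextrin effect divided by that of completers. Neither is in the documents. The all-enrolled effect is (1 − p) + p·r times the completer effect, so

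overstatement = 1/[(1 − p) + p·r] − 1.

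| p | r = 1 | r = 0.5 | r = 0 |
|---|---|---|---|
| 0 | 0% | 0% | 0% |
| 5% | 0% | 1/0.975 − 1 = 2.6% | 1/0.95 − 1 = 5.3% |
| 14.3% (4 of 28) | 0% | 1/0.929 − 1 = 7.7% | 1/0.857 − 1 = 16.7% |
| 20% (6 of 30) | 0% | 1/0.90 − 1 = 11.1% | 1/0.80 − 1 = 25% |

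The last two rows assign every expected dropout to lactose.

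**4. How demanding those rows are.** Assume the six drink orders are used equally. Lactose then comes last in one third of cases, and those people have attended every visit before they could leave because of it. For 4 of 28 to leave, 0.143/(2/3) ≈ 21% of those enrolled would have to be undeclared intolerants who all quit whenever they can. For 6 of 30 the figure is 0.20/(2/3) = 30%.

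**5. What leavers have already supplied.** With the same equal orders, lactose-driven leavers go after visit 1 or visit 2. Half had lactose first and supply that visit only. A quarter had maltodextrin then lactose, which is the whole primary contrast. A quarter had sucrose then lactose, which a mixed model can use.

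**6. What a mixed model recovers.** I took the scenario in step 4 and fitted participant as random with drink and period as fixed effects. The assumed within-person correlation ran from 0.9 down to 0.3, as the documents give none. The model removes roughly 40% to 80% of the overstatement, with the smaller gain at the higher correlation.

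**The case against.** The strongest reply is that tolerators are the intended population. Lactose intolerance is an exclusion, and screening seeks people who can take the drinks. An all-enrolled effect would include some who met an exclusion and were missed. This largely stands. It is why the all-visits model can properly be a sensitivity analysis. It does not answer the lack of visibility: for unrecognised intolerance, behaviour after randomisation decides who counts, in place of an eligibility test.

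A reader might infer that the primary contrast is estimated in tolerators only. The documents do not support that. No rule withdraws people for symptoms, so those who feel unwell but finish stay in, as do those who receive lactose last. Dropouts for unrelated reasons are replaced too.

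A reader might also infer a bias of up to 25%. That needs every dropout to be due to lactose. Section 4.10 takes its 20% from similar studies and does not mention lactose. Other burdens are evident, such as three trial days about four weeks apart, cannulation, and heavy water that can cause dizziness.

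Finally, the plan does not say that leavers' data will be discarded. A person with maltodextrin then lactose could enter the paired t-test for the primary contrast. That is correct, and it shows that the analysis set is undefined. The comparison also remains within-person, so comparability among completers is intact.

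**Conclusion.** The concern holds in a limited form. Self-report screening, a large lactose load in one drink only, replacement until 24 complete, and an analysis with no stated place for partial completers together allow the sample to become enriched for tolerators without this being seen. It is a matter of generalisability and transparent attrition, and does not invalidate the within-person comparison.

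Neither the number of lactose-related dropouts nor their triglyceride response is in the documents, so size and even direction are uncertain. If leavers respond less than completers, a 5% share gives about 3% to 5%; the 8% to 25% range is an upper bound. If dropout is unrelated to the drink, or leavers respond like completers, there is no bias. The change is a cheap improvement and does not repair a demonstrated error.

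**What to change.** Keep rolling replacement and the 24-completer analysis.

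- In section 4.11, define the analysis sets. Prespecify a mixed model for triglyceride iAUC (participant random; drink and period fixed) on all available visits of every randomised participant, except where samples were destroyed at the participant's request. Present it at least as a sensitivity analysis of the lactose-maltodextrin contrast.
- In section 4.8, add a short record of gastrointestinal symptoms and of any unfinished drink at each visit. This cannot be reliably reconstructed later.
- Report all randomised participants, with withdrawals tabulated by last drink taken, period and reason.

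The cost is a few lines of SAP text, a brief form and some extra assays on retained samples. With 4 to 6 leavers and at most two completed visits each, that is no more than 6 × 2 = 12 extra visits. The limitation is that people who leave after one visit add little information, so the selection is reduced and made visible but not removed.

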#### 4.11. Statistical Analyses

All of the analyses subsequently described will first be conducted on the entire sample as a primary analysis (males and females combined). A secondary analysis will include the analysis of subgroups (males only and females only), in addition to exploring sex-by-treatment interaction effects. The distribution of data will be assessed by visual inspection of Q-Q plots in addition to the Shapiro-Wilk test.

#### Primary analyses

Summary statistics (e.g. iAUC, AUC, peak concentrations) will be analysed by one-way ANOVA. Time-course data will be assessed by a two-way (time x treatment) ANOVA. Paired t-tests will be used for post-hoc comparisons, which will be corrected for multiple comparisons using the Holm-Bonferonni adjustment.

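### The stated power of 0.94 leaves out the Holm-Bonferroni correction that the plan applies to its primary contrast; with it, power is about 0.86 to 0.88, below the claimed 90%

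*Combined protocol and SAP*

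**What the plan says.** Section 4.2 defines the primary outcome as one contrast, lactose against maltodextrin, on the 6-hour incremental area under the curve for plasma triglyceride. Section 4.3 uses the same contrast for the secondary outcomes. Sucrose is the third drink (section 4.1, Table 1), so there are three pairwise comparisons.

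Section 4.10 states: "Using this effect size (d = 0.75), 24 participants would provide a >90% probability (power = 0.94) of detecting such an effect". It attributes this to a one-way repeated-measures ANOVA at an alpha of 0.05, "accounting for post-hoc comparisons of three factors by the principle of closed testing". Dropouts are to be replaced until 24 participants have completed.

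Section 4.11 (Primary analyses) plans a one-way ANOVA for summary measures such as iAUC. It continues: "Paired t-tests will be used for post-hoc comparisons, which will be corrected for multiple comparisons using the Holm-Bonferonni adjustment". No section says that the primary contrast is tested outside this correction.

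**The concern.** The two sections do not describe the same test. Section 4.10 says the cost of three comparisons is already inside the 0.94. Section 4.11 then sets a procedure whose first two steps use 0.05/3 = 0.0167 and 0.05/2 = 0.025, and a power that equals the uncorrected figure cannot contain that cost.

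Two things are at stake. First, the claim of more than 90% power for the only primary comparison may be wrong for the analysis as written. Second, the plan leaves open whether the primary p-value is the raw or the Holm-adjusted one. A raw p-value between about 0.017 and 0.05 could be significant under one reading and not under the other, so this should be settled before the data are seen.

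**Working it through.** **Inputs.** From section 4.10: d = 0.75, read as the mean paired difference divided by its SD; n = 24 completers; alpha 0.05. Sidedness is not stated, so two-sided is assumed. From section 4.1: three drinks, hence three pairs. From section 3: the sucrose effect is expected to be similar to that of lactose.

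**Step 1: reproduce the plan's figure.** A paired t-test has df = 24 − 1 = 23 and noncentrality 0.75 × √24 = 3.674. Power is the probability that |T| exceeds the critical value, where T is noncentral t:

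| Two-sided level | Critical t (df 23) | Power |
|---|---|---|
| 0.05 | 2.069 | 0.9403 |
| 0.025 (second Holm step) | 2.398 | 0.8903 |
| 0.0167 (first Holm step) | 2.582 | 0.8526 |

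The stated 0.94 matches the first row, which has no correction.

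**Step 2: power of the planned procedure.** Holm's power for one contrast depends on the other two p-values, so it was simulated: 400,000 trials per scenario, n = 24, compound symmetry, SD of every paired difference = 1, lactose effect 0.75 relative to maltodextrin. The last column shows a closed test for comparison: omnibus F at 0.05, then each pair at the full 0.05.

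| Sucrose effect (SD units, relative to maltodextrin) | No correction | Holm over three | Holm after a significant omnibus F | F-gated closed test |
|---|---|---|---|---|
| 0.75 (equals lactose) | 0.940 | 0.881 | 0.879 | 0.929 |
| 0 (equals maltodextrin) | 0.940 | 0.882 | 0.880 | 0.930 |
| 0.375 (midway) | 0.941 | 0.860 | 0.852 | 0.895 |
| 1.1 (clearly above lactose) | 0.940 | 0.913 | 0.913 | 0.940 |

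Further runs at other sucrose means show that Holm reaches 0.90 only when sucrose lies outside the range between the other two drinks by about 0.2 SD or more: 0.898 at 0.95, and 0.900 at −0.2.

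**Step 3: size of the shortfall.** The miss rate is 1 − 0.940 = 0.060 as stated. Under Holm it is 1 − 0.88 = 0.12 to 1 − 0.86 = 0.14, about twice as high.

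**Step 4: completers needed if Holm is kept.** For power 0.90: 26 if sucrose equals lactose (0.912; 25 gives 0.896) and 27 if sucrose is midway (0.906; 26 gives 0.891). Keeping 0.94 in the worst case, where the contrast must pass at 0.0167, needs 31 (30 gives 0.934).

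**The case against.** The strongest reply is that section 4.10 invokes closed testing, and that 0.94 is nearly right for one such procedure. With three treatments, any two pairwise equalities imply the third. A closed test that starts with the omnibus F can therefore test each pair at the full 0.05, and it gives 0.93 under the protocol's hypothesis. This part stands: a numerical match does not prove which calculation the authors ran, and the fault is a mismatch between two sections rather than an arithmetic slip. It does not rescue the plan, because section 4.11 names Holm. Holm is itself a closed procedure, but one built on Bonferroni tests, and 0.94 does not include their cost. Even a generous reading that uses the logical relation among the three pairs (smallest p-value below 0.0167, then each pair at 0.05) gives 0.91 if sucrose equals lactose and 0.87 if it is midway.

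A second reply is that the loss is modest. Holm controls the familywise error, the treatment estimate is unchanged, 0.86-0.88 is a power many trials accept, and 0.90 needs only two or three more completers. That is fair, and no bias or excess of false positives is alleged. But the protocol justifies its sample size by exceeding 90% and says that multiplicity was counted.

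Third, the hypothesis in section 3 covers sucrose as well, so correcting across all three pairs is a legitimate choice. It is, provided that the stated power reflects it.

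Fourth, d = 0.75 is itself uncertain. It rests on pilot data for galactose versus glucose over 300 minutes (the pilot figure gives n = 10), and the printed 46.51 ± 0.28 does not yield it (46.51 / 0.28 is about 166). At d = 0.67 even the uncorrected test has power of only 0.88. That is a separate problem and may be as large, but at any given d the Holm correction cannot raise power above that of the uncorrected test.

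**Conclusion.** The concern holds. The stated 0.94 is the power of an uncorrected two-sided paired t-test at d = 0.75 and n = 24. Under the Holm correction that section 4.11 prescribes, power for lactose versus maltodextrin is 0.88 under the protocol's own hypothesis and 0.86-0.88 wherever sucrose lies between the other two drinks. That is 6 to 8 percentage points lower and below the claimed 90%. Adding an omnibus gate makes it 0.85-0.88. The range rests on d = 0.75, a two-sided alpha of 0.05, 24 completers and compound symmetry. It would exceed 0.90 only if the sucrose mean fell clearly outside the range of the other two.

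**What to change.** In section 4.11, state that lactose versus maltodextrin on triglyceride iAUC is the single primary test, done at two-sided 0.05 with no omnibus gate and no Holm adjustment. Apply Holm only to lactose versus sucrose and sucrose versus maltodextrin. The 0.94 is then correct for d = 0.75 and 24 completers, and section 4.10 should describe this test in place of closed testing. If familywise error of 0.05 is wanted across all three contrasts, test the two sucrose contrasts only after the primary test succeeds. Without that condition the bound is 0.05 + 0.05 = 0.10.

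There are two acceptable alternatives. One is to write the F-gated closed test into section 4.11 and state a power of about 0.93 under the hypothesis (0.90 if sucrose is midway). The other is to keep Holm over all three and restate the power as about 0.88, with 0.85 at the first Holm step, or plan 26 to 27 completers to keep 0.90.

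The recommended change costs wording only and needs no extra participants, but it ranks the sucrose contrasts explicitly below the primary one. It should be made before anyone sees the outcome data by treatment; the documents do not show whether that is still possible.
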